*Usual Care Group:* The comparison group, those randomized to usual care (UC), will receive referrals to services at the time of enrollment. The usual care group will not receive the POISED structured assessment, attention to chronic disease management, or RCA related to the ED visit. Similar to intervention group, we will provide UC patients with a laminated card showing the Stress Thermometer™ (Appendix 5) for use in follow-up interview assessments.

**Specific Aim 1 Measures – Emergency Department (ED) Use:** We will obtain consent from patients to enable review of their medical records. We will identify all ED visits for the year prior to the index ED visit/study enrollment and for one year after enrollment. We will also search all-payer databases (APD) New York and the Indiana State Network for Patient Care to identify any episode of ambulatory or acute care that occurred within the 6 months of enrollment (6-month intervention and 6-month follow-up) and the 12 months prior to enrollment. Using the Care Recipient medical records, we will determine any prior diagnoses of dementia. We will also use the Care Recipient's medical records to determine comorbidity and root cause for ED use.

A one-item survey question will identify any additional visits that might have occurred outside the indicated state regions. For descriptive purposes, ICD discharge diagnoses will be included for any ED use. We will structure continuous variables that describe the number of ambulatory and/or acute care episodes.

**Aim 2: Develop a collaborative care plan with the interventional group and schedule follow up testing to assess whether the 6-month POISED intervention will improve family caregiver “activation” in managing the health care of care recipients compared with post-ED care without POISED at 3 and 6 months.**

*Strategy:* The POISED care management team consisting of specially-trained nurses functioning as care managers (CMs) and para-professionals in the role of care manager assistants (CMAs) will work to create an individualized care plan through the lens of cognitive impairment with an emphasis on coordinating care with the patient's primary care provider (PCP) and achieving relevance with the goals and capacity of the family CG and CR.

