#### Statistical Plan

We will compare randomization results to the pre-planned schedule, to ensure randomization integrity. To verify the comparability of the randomized groups, we will compare dyads to identify differences between their baseline characteristics (age, gender, race, education), CR comorbid medical conditions, and the Charlson comorbidity index. We will also look for differences in the number of primary care visits and acute care use during the year prior to enrollment between POISED and the usual care group by using analysis of covariance (ANCOVA) models for continuous variables and the Cochran-Mantel-Hansel statistic for categorical variables. We will control for stratification variables: recruitment site (NYU or IU), English vs Spanish (at NYU site), living arrangement (CG lives with CR or not), and cognitive status (Mini-CogTM score of a 3 or less). A cutoff of 0 or 1 is more strongly associated with functional disability than a cutoff of 3. Subjects requiring the IQ-CODE with scores  $>3.4$  will be included with those with MiniCogTM scores =0 to reflect greater impairment for those who cannot complete the Mini-CogTM. We will examine the distributions of continuous variables and use transformation or nonparametric methods in cases of violation to the normal distribution assumption. We will also examine the frequency distribution of all categorical variables and use exact inference procedures in cases of zero or small cell size. We will use SAS 9.4 (SAS Institute, Carey, North Carolina) for all analyses.

Specific Aim 1: We will use logistic regression models to compare the rates of ED admissions during the 6-month intervention period following the index (recruitment) ED visit. ED readmission within 6 months will be used as a binary outcome in the logistic model and randomization group will be the independent variable while adjusting for all stratifying variables including site, language, living arrangement and CR cognitive status. Baseline characteristics that are shown to be unbalanced in univariate comparisons between the two groups will also be adjusted.

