Specific Aim 2: We will use mixed effects models with CG activation scores at 3 months and 6 months as the outcome measure and randomization group as the independent variable while controlling for baseline activation score and stratification variables (site, language, living arrangement and CRs' cognitive status). We will conduct post-hoc comparisons of the activation scores between the POISED group and the usual care group at 3 and 6 months using linear contrast from the mixed effects model following a significant group effect. To explore what changes are responsive to the POISED intervention, we will also use the mixed effects model to examine differences in activation domain scores between the two groups. The mixed effects

model will account for potential correlations between repeated measures from the same individual and deal with missing data appropriately when the probability of missing data is unrelated to the missing observation.

Specific Aim 3: We will use mixed effects models with repeatedly measured PHQ-9, GAD-7 and MOS social support scores collected at 3 and 6 months as dependent variables. The independent variable for the mixed effects model will be the indicator variable for the randomization group while controlling for baseline scores and stratification variables. We will use post-hoc analysis to determine group differences in these measures between the two groups at the 3- or 6-month evaluations. The modeling approach resembles that for Aim 2.

Sensitivity analysis for missing data: The analysis plan outlined above assumes that outcome measures at follow up are missing at random with respect to demographic characteristics and baseline results. We will compare baseline characteristics of subjects with missing outcomes due to death or withdrawal to detect potential violation of the missing-at-random assumption. Further sensitivity analyses will involve various imputation methods or a full parametric likelihood approach that assumes various patterns of missing data.

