## Appendix 1: Data Variables

Table 1: Measures			
Measure	Data Source	Measure Construction	Measures refer to: CG* and / or CR*; Assessment times: 0/BL † , 3, 6, 12 month
Predisposing Fixed Characteristics			
Basic			
Age	EMR/ Survey	Years	CG, CR; 0 mo. (BL)
Gender	EMR/ Survey	Categorical: Male/Female	CG, CR; 0 mo. (BL)
Race/Ethnicity	EMR/ Survey	Categorical: White, Black, Hispanic, other	CG, CR; 0 mo. (BL)
Education	Survey	Categorical: < H.S., H.S., Some College, College graduate+	CG; 0 mo. (BL)
Prior (1-year) non-acute use	EMR/ Survey	Counts: physician ambulatory visits, in-home supportive services	CR; 0 mo. (BL)
Prior (1-year) acute use	EMR/ Survey	Counts: physician ambulatory visits, ED, hospital visits / bed days	CR; 0 mo. (BL)
ADRD-Specific			
Dementia Type	EMR	Categorical: including AD, Lewy Body disease, Parkinson's Disease, Vascular, Frontotemporal, and mixed	CR; 0, 3, 6 mo.
Caregiver relationship to CR	Survey	Categorical: Spouse, child, other relative, friend/other	CG, CR; 0 mo.
Functional State	Survey	14 items: ADL/IADL for CG; within HABC-M ‡ for CR	CG, CR; 0, 3, 6 mo.
Marital Status	Survey	Categorical: Single/never married, married, divorced, widowed	CG, CR; 0, 3, 6 mo.
Substance use history	Survey	Current: Yes/No; Past history: Yes/No	CG, CR; 0, 3, 6 mo.
Mental illness history	Survey	Yes/No: Depression, schizophrenia, PTSD, other	CG, CR; 0 mo.
Enabling Time Varying Effect Characteristics			
Basic			
Distance to hospital (ED)	Calculated	Miles	CG, CR; 0, 3, 6 mo.
Distance to usual source of care (USC)	Calculated	Miles	CG, CR; 0, 3, 6 mo.
Difference in distance ED vs. USC	Calculated	Miles (USC) – distance to hospital	CG, CR; 0, 3, 6 mo.
Change in PCP	Survey	Yes/No	CR; 0, 3, 6 mo.
Insurance	EMR	Yes/No	CR; 0, 3, 6 mo.
Current non-acute use	EMR/ Survey	Counts: physician ambulatory visits, in-home supportive services	CR; 0, 3, 6, 12 mo.
Current acute use	EMR/ Survey	Counts: physician ambulatory visits, ED, hospital visits / bed days	CR; 0, 3, 6, 12 mo.
ADRD-Specific			
Mode of transportation	Survey	Categorical: personal car, taxi, train, bus, walk	CR; 0, 3, 6 mo.
Caregiver living arrangement	Survey	Categorical: Live with subject, close proximity (miles), other	CG; 0, 3, 6 mo.
Caregiver stress	Survey	Stress thermometer (scale), 5-level visual analogue scale *	CG; 0, 3, 6, 12 mo.
Dementia symptoms	Survey	HABC-M ‡ (measuring severity of CR symptoms)	CR; 0, 3, 6 mo.

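### The Aim 1 model picks covariates by baseline imbalance with no stated cut-off, and leaves prior-year ED use, already collected, to enter by chance

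*Combined protocol and SAP*

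**What the plan says.** Under Statistical Plan, Specific Aim 1, ED readmission within 6 months is a binary outcome in a logistic model. The model has randomised group and the stratification variables (cognitive status, living arrangement, language, site). One further sentence follows: "Baseline characteristics that are shown to be unbalanced in univariate comparisons between the two groups will also be adjusted".

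The opening paragraph of the same section describes the baseline comparisons: "we will compare dyads to identify differences between their baseline characteristics (age, gender, race, education), CR comorbid medical conditions, and the Charlson comorbidity index". It continues: "We will also look for differences in the number of primary care visits and acute care use during the year prior to enrollment". The tools are "analysis of covariance (ANCOVA) models for continuous variables and the Cochran-Mantel-Hansel statistic for categorical variables", with control for the stratification variables.

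The other aims are handled differently. The Aim 2 model is fitted "while controlling for baseline activation score and stratification variables", and the Aim 3 models "while controlling for baseline scores and stratification variables".

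Prior ED use is collected in three places:

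- Specific Aim 1 Measures (records): "We will identify all ED visits for the year prior to the index ED visit/study enrollment".
- Appendix 1, Table 1, where prior-year acute use is a baseline item built as "Counts: physician ambulatory visits, ED, hospital visits / bed days".
- Appendix 3, where the baseline survey asks the caregiver for the number of ED visits over the last 12 months. Recruitment, Consent and Assent places randomisation after this interview.

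**The concern.** An analyst cannot fit the Aim 1 model from the text alone, because three items are missing.

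1. **Cut-off.** No p-value, standardised difference or other criterion defines imbalance. The 0.05 level appears only in the power section.
2. **Candidate list.** The opening paragraph names variables to compare, but the Aim 1 rule does not refer to that list, and Table 1 holds many more baseline measures.
3. **Test.** The planned comparisons control for the stratification variables, while the rule speaks of univariate comparisons. Whether these are the same tests is not said.

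The criterion is also the wrong one. Under valid randomisation, imbalance is chance. It can bring in variables unrelated to ED return and leave out a strong predictor that happens to be balanced. Prior-year ED use is the obvious candidate predictor, and its use in the primary model is left to luck. At stake are a fixed primary analysis and some efficiency.

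**Working it through.** **The plan's own figure.** Inputs from Sample Size and Power Consideration: 320 per group, control rate 40%, odds ratio 0.62, level 0.05 (taken as two-sided).

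- Odds in POISED: (0.40/0.60) × 0.62 = 0.4133, so p2 = 0.4133/1.4133 = 0.2925.
- Mean rate 0.3462. SE under the null: √(2 × 0.3462 × 0.6538/320) = 0.0376. SE under the alternative: √((0.40 × 0.60 + 0.2925 × 0.7075)/320) = 0.0374.
- Power = Φ((0.1075 − 1.96 × 0.0376)/0.0374) = 81.7%. With p2 = 0.29 it is 83.5%.

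The stated 82% reproduces.

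**How often the rule acts.** Under randomisation a variable is flagged at cut-off t with probability t, so prior use enters in about 5%, 10% or 20% of trials at t = 0.05, 0.10 or 0.20. Counting eight named candidates (age, gender, race, education, comorbid conditions, Charlson index, primary care visits, acute care use) as independent, the chance of at least one flag is 1 − (1 − t)^8:

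- t = 0.05: 34%
- t = 0.10: 57%
- t = 0.20: 83%

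With four of them correlated, simulation gives 32%, 54% and 81%.

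**Power, by simulation.** The documents give no association between prior use and return visits, so it is varied. Assumptions:

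- Prior-year count negative binomial (mean 1.5, size 1), entered as standardised log(count + 1).
- Seven other candidates, none prognostic.
- Stratified block randomisation, with the stratification variables in every model.
- Marginal rates 0.40 and 0.2925; imbalance judged by t-test; Wald test for arm.
- 10,000 runs per setting. The standard error of one power figure is about √(0.82 × 0.18/10,000) = 0.4 points.

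| Per arm | Assumed OR per SD | Stratification variables only | Rule at 0.05 | Rule at 0.20 | Prior use fixed | Gain over 0.05 rule |
|---|---|---|---|---|---|---|
| 320 | 1.25 | 82.1% | 81.9% | 81.7% | 82.5% | 0.6 |
| 320 | 1.5 | 82.2% | 82.1% | 82.3% | 83.4% | 1.3 |
| 320 | 1.8 | 81.7% | 82.0% | 82.4% | 84.5% | 2.5 |
| 320 | 2.5 | 82.7% | 83.2% | 84.4% | 88.1% | 4.9 |
| 320 | 2.7 | 81.7% | 82.4% | 83.4% | 88.3% | 5.9 |
| 450 | 1.25 | 92.8% | 92.7% | 92.7% | 92.9% | 0.2 |
| 450 | 2.7 | 92.5% | 93.1% | 94.0% | 96.4% | 3.3 |

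The 450 rows take the 900 dyads in Methods, Aim 1, split equally.

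A simpler simulation used one normal covariate, no stratification variables, and 40% against 29%. For log odds ratios of 0.3, 0.5, 0.8 and 1.0 per SD, power with the covariate fixed was 83.6%, 84.5%, 87.1% and 89.4%. Under the 0.05 rule it was 83.2%, 83.3%, 83.4% and 84.5%. The gains are 0.4, 1.2, 3.7 and 4.9 points.

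**Type I error.** With the rule applied mechanically, null rejection was 4.2% to 5.1% in the main simulation and 4.4% to 5.2% in the simpler one. With prior use fixed it was 5.0% to 5.4% in the main simulation.

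**Sensitivity to the cut-off.** Comparing no addition with rules at 0.05, 0.10 and 0.20, the significance verdict was not the same for all four in 2.7% to 5.3% of trials at 320 per arm, and in 1.1% to 2.7% at 450.

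**The estimand.** Conditional odds ratios matching the marginal 0.62 are 0.617, 0.609, 0.596, 0.565 and 0.557 for the five assumed associations. Adding prior use raises the mean SE of the log odds ratio from 0.169 to between 0.170 and 0.189, but the effect itself moves further from zero. On the standardised risk-difference scale the SD falls from 0.0370 to 0.0369 (OR 1.25) or from 0.0375 to 0.0342 (OR 2.7).

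**The case against.** The harm is small. The stated power is right, a mechanical rule keeps the type I error, and at odds ratios of 1.25 to 1.5 per SD the gain is only 0.6 to 1.3 points. The larger gains need an association for which the documents offer no support. All of this stands.

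The count of eight is a reading of the text. Age, gender and race are listed for both members of the dyad, and comorbid conditions may be several variables. Eleven independent candidates would give 43%, 69% and 91%. The verdict-change figures include a no-addition analysis that is not the plan, and 0.20 is only an illustrative cut-off. The simulation used t-tests and treated the other candidates as non-prognostic. These points limit the precision of the figures. They do not supply the missing cut-off.

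The rule may be meant to point back to the opening paragraph, and prior-year acute use is among the variables compared there. It is therefore considered, but its entry still depends on a chance difference.

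A 12-month count is also not the same measure as any visit in 6 months, so the parallel with Aims 2 and 3 is not exact. That is fair. It remains the nearest baseline counterpart the study collects.

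Finally, the survey count is a limited fallback. Where record access is refused, the main source of the Aim 1 outcome is missing too. Rewording the item after enrolment has begun would also make answers differ between participants.

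**Conclusion.** The point holds. The primary Aim 1 model is not fixed in advance: the cut-off is absent, and the candidate set and test are not tied to the rule. Prior-year ED use enters only by chance. This is not an error in the sample size, and nothing here shows inflated type I error for a cut-off set beforehand and applied mechanically.

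The textual gap is certain. The efficiency loss is conditional: 0.6 to 5.9 points of power at 320 per arm against a 0.05 rule (0.2 to 3.3 at 450), for assumed odds ratios of 1.25 to 2.7 per SD. Fixing the model would be reason enough to change the text even if the gain were nil.

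**What to change.** 1. Remove the imbalance rule from the primary Aim 1 model. If it is kept, make it a sensitivity analysis with a stated cut-off, test and variable list. Report baseline comparisons descriptively.
2. Pre-specify arm, site, language, living arrangement, cognitive status and prior-year ED visits, for example as log(count + 1), with the index visit excluded. Name the ED count alone, since the Table 1 item mixes it with ambulatory visits, hospital visits and bed days.
3. Take the count from records where access is granted, and otherwise from the caregiver's baseline 12-month report. State one rule for a missing covariate. The fallback helps only participants whose Aim 1 outcome is available.
4. If practicable, word the survey item to exclude the present visit. Do not subtract one afterwards, because some caregivers will have counted that visit and others not.
5. Optionally report a standardised risk difference beside the odds ratio, and note that the adjusted odds ratio is conditional and will differ from the marginal 0.62 used for power.

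The cost is low: wording in the Statistical Plan, one source and missing-covariate rule, and at most one survey clarification. No new data or change in sample size is needed.

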### **METHODS**

**Setting:** The study will be conducted in two cities, New York and Indianapolis, in the EDs of their respective academic institutions—NYU Langone Medical Center and Indiana University Health University Hospital. The NYU Ronald O. Perleman Center for Emergency Services sees >60,000 patients annually. In 2015 the numbers of ED patients >75 years who were discharged to home were >3700 in the NYU ED and 2400 patients in the Indiana University Eskanazi and Methodist EDs.

**Aim1: Recruit and randomize a sample of 900 patient-caregivers (CGs) dyads (1800people total) presenting to the ED and test whether the POISED intervention will reduce recurrent acute care use over 6 months when compared with post-ED care for patients and CGs without POISED.**

**Study Design:** We will randomize subjects to either usual care or interventional groups where we will perform an initial assessment and provide a novel care management intervention for family CGs of ED users with cognitive impairment and likely ADRD.

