*Randomization:* A web-based randomization scheme will be used to randomize participants to intervention or usual care groups in blocks of four or six stratified by: site (NYU or IU), English or Spanish speaking, whether the care partner lives with the CR, and Mini-Cog™ score less than or equal to 3 (or IQCODE of >3.4).

. We assume a positive IQ-CODE score (>3.4) with an inability to complete a Mini- Cog™ is equivalent to a Mini-Cog™ score of 0.

*Initial assessment phase:* The POISED care management team consisting of specially-trained nurses functioning as care managers (CMs) and para-professionals in the role of care manager assistants (CMAs) will conduct a biopsychosocial/environmental needs assessment by phone within 48 hours of emergency room discharge if not possible during the ED stay. These team members are clinical professionals delivering a clinical service. They are not research staff or delivering experimental procedures. This assessment includes a demographic and psychosocial interview focused on achieving problem identification. The program uses standardized assessment tools including "Managing Your Loved One's Health" (MYLOH™) for chronic disease management and BEHAVE 5+ to identify problem behaviors common in advancing dementia that have been associated with caregiver strain, challenges to caregiving at home and in long-term care. BEHAVE 5+ also identifies proven behaviors common in prescribing of psychotropic medications to people with dementia. (See Appendix 3) If the consented CG is not available, we will attempt to complete the CG questions at a later date either by phone or in person.

*Root Cause Analysis:* Starting with the ED visit and working backwards in time, the team will explore and identify problems or branch-point situations that progressed to the need for ED care. Using a logic tree as a cause and effect approach to create a timeline of events leading to ED visit and asking the question, "how could this occur?" or "why" based on the "Five-Whys" strategy, the CM team will ask "why" for each successive answer, starting with "why did you come to the ED." Answers will be applied to medical record review looking for other possible triggers and opportunities for intervention. This brainstorming/investigative process to improve quality is also deployed by patient safety teams investigating adverse events.

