Sample Size and Power Consideration: Sample size for the proposed study is estimated for achieving 80% power in reducing acute care use in the POISED group compared with the usual care group in Specific Aim 1. A previous study had reported a 30-day readmission rate of 58% in dementia patients as compared to 38% in those without dementia. Given that our patient sample may include less severe cognitive impairment with less ED use, we assume, conservatively, that the rate of ED visits in the usual care group is 40%. With 320 patients enrolled per group, we will have 82% power to detect an odds ratio of 0.62 for repeat ED visits in the POISED group compared to the usual care group at the 0.05 significance level. This detectable odds ratio is equivalent to reducing the ED visit rate to 29% or lower in the POISED group compared with the 40% assumed for the control group. The use of stratified randomization ensures that patients in the intervention and control groups are similar on the stratification variables, thus reducing the variance of the difference between the two group means and resulting in greater power than simple randomization. Therefore, actual power for our study will be higher than projected here. Since we will be using EMR for acute care data and phone follow-up to supplement out of network use, we anticipate complete data from all study participants for this aim.

For Aims 2 and 3, assuming that 205 (64%) dyads will complete the 6-month evaluation (see Figure 2), we will have 80% power to detect an effect size of 0.28 or greater on the CG activation score, PHS-9, GAD-7 and MOS scores between POISED group and the control group using a two-sample t-test at the 0.05 significance level. The detectable effect size of 0.28 used in our power estimation is reasonable and justified given that previous studies on collaborative care management of dementia patients have shown an effect size of 0.45 SD on a number of caregiver psychosocial outcomes. Our previous studies have found a mean PHQ-9 score of 4.4 (SD=5.6), and a mean GAD-7 score of 3.2 (SD=3.5). Thus our projected effect size will allow us to detect a change as small as 1.6 on the PHQ-9 and 1 on the GAD-7. As described above, the use of stratified randomization will provide greater power than those projected here.

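### No analysis allows for care-manager teams shared within the POISED arm; if outcomes vary by team, standard errors will be too small, and the claim of higher-than-projected power is unsupported

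*Combined protocol and SAP*

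**What the plan says.** Dyads are randomized individually (Methods, Randomization). In the intervention arm they are assessed, given a care plan and followed for six months by a team of "specially-trained nurses functioning as care managers (CMs) and para-professionals in the role of care manager assistants (CMAs"). The usual care group gets referrals and none of the POISED assessment or root cause analysis (Methods, Usual Care Group).

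The Statistical Plan sets these models:

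- **Aim 1:** logistic regression of any ED return within 6 months on arm, the stratifiers and any unbalanced baseline variables.
- **Aim 2:** a mixed effects model adjusted for the baseline score. The only correlation it names is within person: the "model will account for potential correlations between repeated measures from the same individual".
- **Aim 3:** the same approach as Aim 2.

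The power paragraph assumes independent dyads. "With 320 patients enrolled per group", it says, "we will have 82% power to detect an odds ratio of 0.62 for repeat ED visits". It then argues that stratified randomization reduces variance and concludes: "Therefore, actual power for our study will be higher than projected here". It says the same for Aims 2 and 3. The Methods section gives a different target: "Recruit and randomize a sample of 900 patient-caregivers (CGs) dyads".

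No section gives the number of care managers, a caseload, an ICC, a team term or a robust standard error.

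**The concern.** The protocol gives the care team real discretion over what a dyad receives. The team tailors the care plan, sets the intensity of contact by need, may make a home visit to head off an ED visit, and prioritizes dyads when demand exceeds capacity (Methods, Aims 2 and 3; Appendix 4). It is therefore plausible that some teams do better than others, and that dyads sharing a team have correlated outcomes. Adjusting for site as a common effect in both arms does not absorb differences between teams within one arm.

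A model that treats POISED dyads as independent counts between-team variation as information about the programme. A result driven by one or two strong or weak teams could then be read as a programme effect. The power statement adds to this, because it counts one possible gain and leaves out this possible loss.

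**Working it through.** **Inputs from the power paragraph.** 320 per group; usual care rate 0.40; odds ratio 0.62; 0.05 level (two-sided assumed; one-sided would give 88.9% power). For Aims 2 and 3: 205 completers per group and effect size 0.28 SD. From Methods: 900 dyads, or 450 per arm at 1:1.

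**Assumptions not in the documents.** K = 4 to 10 teams of equal caseload, ICC 0.01 to 0.02, clustering in the POISED arm only. All results use a normal approximation without small-cluster degrees of freedom; with few teams that correction would lower power further.

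**Step 1: reproduce the plan.** Usual care odds are 0.40/0.60 = 0.667. Times 0.62 this is 0.413, so the POISED rate is 0.413/1.413 = 0.2925 and the difference is 0.1075. The binomial variances are 0.24 and 0.2069. SE = √[(0.24 + 0.2069)/320] = 0.0374; 0.1075/0.0374 = 2.88; power = Φ(2.88 − 1.96) = 82.1%. A pooled variance gives 81.7%. For Aims 2 and 3, SE = √(2/205) = 0.0988; 0.28/0.0988 = 2.835; power = Φ(0.875) = 80.9%. The stated 82% and 80% are correct under independence.

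**Step 2: Aim 1 with 320 per arm.** Let m = 320/K and DE = 1 + (m − 1) × ICC, applied to the POISED arm.

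- True over naive variance at a zero average effect: (1 + DE)/2.
- Rejection probability of the naive test: 2[1 − Φ(1.96/√((1 + DE)/2))].
- Power with a correct SE: SE = √[(0.24 + DE × 0.2069)/320].

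| Teams | ICC | m | DE | Rejects a zero average effect | Power |
|---|---|---|---|---|---|
| any | 0 | – | 1.00 | 5.0% | 82% |
| 4 | 0.01 | 80 | 1.79 | 9.7% | 69% |
| 4 | 0.02 | 80 | 2.58 | 14.3% | 59% |
| 8 | 0.01 | 40 | 1.39 | 7.3% | 75% |
| 8 | 0.02 | 40 | 1.78 | 9.6% | 69% |
| 10 | 0.01 | 32 | 1.31 | 6.8% | 77% |
| 10 | 0.02 | 32 | 1.62 | 8.7% | 72% |

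Inflating both arms' variance equally, from the pooled 81.7%, gives 57% to 76% instead of 59% to 77%. Two teams at ICC 0.01 (m = 160, DE = 2.59) would match four teams at 0.02.

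**Step 3: Aim 1 with 450 per arm.** Without clustering, power is 93%. The worst case (4 teams, ICC 0.02) has m = 112.5, DE = 3.23, SE = √[(0.24 + 3.23 × 0.2069)/450] = 0.0449 and power 67%. The best case (10 teams, ICC 0.01) has m = 45, DE = 1.44, SE = 0.0346 and power 88%. The larger sample helps power but not the rejection rate: with 8 teams at ICC 0.02 it rises from 9.6% to 11.6%, because caseloads grow.

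**Step 4: Aims 2 and 3.** With the unadjusted t-test of the power paragraph and m = 205/K, the rejection rate is 6.1% to 11.0% and power 64% to 77%. The planned model, however, adjusts for the baseline score. With baseline-to-follow-up correlation ρ (an assumption) and the team variance left unreduced, the variance of the difference is [2(1 − ρ²) + (m − 1) × ICC]/205. For 4 to 10 teams:

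- ρ = 0.5: power 81% to 87% at ICC 0.01, 72% to 83% at ICC 0.02.
- ρ = 0.4: power 77% to 83% at ICC 0.01, 69% to 80% at ICC 0.02.

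Baseline adjustment does not bring the rejection rate back to 5%. At ρ = 0.5, 4 teams and ICC 0.02, true over naive variance is (1.5 + 50.25 × 0.02)/1.5 = 1.67, so the naive test rejects 2[1 − Φ(1.96/√1.67)] ≈ 13% of the time.

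**Step 5: the gain the plan counts.** If the strata explain 2% of the outcome variance (an assumption), SE shrinks by √0.98 and Aim 1 power goes from 82.1% to 82.8%.

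**The case against.** A reader might infer that the standard errors are certainly too small. The documents do not support that. It needs ICC above 0 and a conclusion that reaches beyond the care managers employed here. With ICC near 0 the effect is negligible, and if inference is limited to these staff the naive standard error can be defended. Both points stand. However, the Specific Aims look to strategies for wider use, which is a claim about the programme.

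A reader might also take the 7% to 14% as the type I error when POISED does nothing for anyone. It is not. If no dyad is affected, teams cannot create correlation through treatment, and individual randomization keeps the test near 5%. The figures apply when some teams help and others harm, averaging to zero.

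Nor do the documents show that power must fall below the projection. At 450 per arm with ICC 0.01 and 6 to 10 teams, Aim 1 power is 84% to 88%. Baseline adjustment can lift Aims 2 and 3 above 80%. The plan makes neither argument, though; it cites stratification alone.

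Two further objections limit the remedy. The documents do not say that a dyad stays with one care manager, and follow-up is mainly by the assistant. With one team per site a team variance could hardly be estimated. Usual care may also share providers: Specific Aim 3 describes its comparator as referred to other care management programmes. These are good reasons not to impose a POISED-only random effect as the primary model. They do not justify leaving the team out of the plan altogether.

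**Conclusion.** The point holds conditionally. The documents show teams shared by POISED dyads, no POISED care manager in usual care, and no allowance for team in any of the three aims. If team outcomes vary and the conclusion is about the programme, the planned standard errors will be too small. The ranges calculated above rest on assumed ICCs and team counts and are not estimates for this trial.

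One part needs no assumed ICC: the unqualified statements that actual power will be higher are unsupported, because they count a stratification gain and ignore a possible clustering loss. There is no arithmetic error in the stated 82% and 80%. This is a cheap improvement that should be made; it does not invalidate the design.

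**What to change.** - Record the responsible care manager and assistant (team ID), with dates of any reassignment, for every POISED dyad. The tracking system under Data Collection and Documentation already takes the team's entries, so this is one retained variable. It may be hard to reconstruct later.
- Keep the stated primary models.
- For all three aims, pre-specify a partially nested sensitivity analysis with a team effect in the POISED arm and small-sample degrees of freedom. If there are too few teams to estimate the variance, recalculate the standard errors over a stated ICC range instead.
- State the expected number of teams and the caseload.
- Reconcile 900 dyads with 320 per group, and replace both higher-power sentences with power at ICC 0, 0.01 and 0.02 for the reconciled size.

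The cost is SAP wording, a little more analysis, wider intervals in the sensitivity analysis and a less favourable stated power. With very few teams those intervals could be much wider, which is why the analysis is proposed as a sensitivity analysis.
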